**Table 1 Windowing for longitudinal data**

Month	Target Study Day	Lower (Day)	Upper (Day)
3	91	46	135
6	182	136	225
9	273	226	315
12	365	316	405
15	456	406	495
18	547	496	585
21	638	586	675
24	730	676	765
27	821	766	855
30	912	856	945
33	1003	946	1035
36	1095	1036	1125
39	1186	1126	1215
42	1277	1216	1305
45	1368	1306	1395
48	1460	1396	1485
51	1551	1486	1575
54	1642	1576	1665
57	1733	1666	1755
60	1825	1756	1845

When a subject has multiple usable records within a window then the record nearest the target day will be used, and when two are equal distant from the target day, different days, then the later will be used. Lastly, if multiple values are on the same day then mean value (if numeric data) or the mode (if categorical data) will be used.

#### 7.1.4 Conventions for Incomplete or Missing date of ENANTONE Therapy

The date of the first ENANTONE administration is necessary for establishing the chronology of all subject data. Likewise, the date for the last administration of ENANTONE has similar importance for indexing subject data. If the month and year are available but the day of administration is missing, an imputed date will be used in the derived data. The imputed day will be in the middle of the month with a date of the 15th of that month chosen as the imputed date. The imputed values will be documented in the data listings alongside the actual recorded date. Because dose scheme may be complicated, based on clinical judgement, other unpredicted special cases will be handled in program with notes documented in the original SAS programs.

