## 7.0 METHODS OF ANALYSIS AND PRESENTATION

### 7.1 General Principles

Statistical analysis will be performed using SAS® software (SAS Institute, Inc., Cary, North Carolina) Version 9.2, or later.

Data will be associated and summarized by the following:

- ENANTONE treatment phase includes all data from the first dose of ENANTONE up to and including either 45 days, inclusive, after the last dose or date of first dose of a non-ENTANTONE GnRH agonist therapy (earliest case scenario)
- Follow-up phase includes all data after the above defined ENANTONE treatment phase. If the subject continued treatment for CPP with another GnRH agonist after ENANTONE, their data from the follow-up period will be reported separately from those who only received ENANTONE for the treatment of CPP.

Unless specified otherwise, all data summaries will be performed for the following groups: Male, Female and Total, and will be presented during the ENANTONE treatment phase and results during the follow-up phase. Continuous variables will be summarized including the number, the mean, the standard deviation, median, minimum and maximum. Categorical variables will be summarized including the number and percentage of subjects.

Confidence intervals will be reported as 2-sided 95%, unless otherwise stated.

Means and medians will be presented to 1 more decimal place than the recorded data and standard deviations (SDs) will be presented to 2 more decimal places than the recorded data. Confidence intervals about a parameter estimate will be presented using the same number of decimal places as the parameter estimate. Derived variables may exhibit excessive decimal precision therefore, derived variables may be rounded to a precision representative of the expected data and means, SD and individual values will be formatted in a similar manner as described above.

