#### 7.1.1 Study Definitions of Baseline and Change from Baseline

Baseline, for the ENANTONE period, is defined as the last non-missing measurement prior to the first dose of ENANTONE treatment. Unless specified otherwise, baseline values for variables related to CPP will be limited to values collected no more than 3 months (93 days), inclusive, prior to the first dose of ENANTONE.

The change from baseline will be calculated for the treatment period by subtracting the baseline values from the individual post-baseline values. If either the baseline or post-baseline value is missing, the change from baseline is set to be missing as well.

Data from the follow-up period after completion of treatment period, will be analyzed separately and the baseline for the follow-up period will be defined as the first non-missing measurement after the last dose of GnRHa treatment (with either ENANTONE or another GnRHa).

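### A missing day of the first ENANTONE dose is set to the 15th without a check against fully dated records, so AEs and assessments close to the dose can fall on the wrong side of it

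*SAP*

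**What the plan says.** SAP 7.1.4 recognises how much hangs on this date: "The date of the first ENANTONE administration is necessary for establishing the chronology of all subject data". The trigger for imputation is simple: "If the month and year are available but the day of administration is missing, an imputed date will be used in the derived data". The value is always the 15th ("The imputed day will be in the middle of the month"), and the imputed date is listed beside the recorded one. The only flexibility is that "other unpredicted special cases will be handled in program with notes documented in the original SAS programs".

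Three definitions then depend on the date:

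- SAP 7.1: "ENANTONE treatment phase includes all data from the first dose of ENANTONE up to and including" the earlier of 45 days after the last dose and the first dose of another GnRH agonist. Follow-up is everything after that, so a record dated before the first dose is in neither phase.
- SAP 7.1.1: baseline "is defined as the last non-missing measurement prior to the first dose of ENANTONE treatment". For CPP variables it must also lie within 93 days before that dose. If baseline is missing, so is the change from it.
- SAP 7.1.2: the first dose is Study Day 1.

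Two neighbouring rules are relevant. SAP 7.1.5 moves an AE with a missing day in the first-dose month to the first-dose date. SAP 7.1.6 does not let an imputed medication or history end date pass the last visit. SAP 7.1.4 has no comparable limit.

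**The concern.** Imputing the dose date moves the time origin of a child's whole record, while AEs and assessments with complete dates stay where they are. The order of a record and the dose can therefore reverse, even when the chart documents that order.

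Both primary outcomes are exposed. The safety outcome is AE incidence per 100 person-years, summarised by phase (SAP 7.11 and 7.11.1), with injection site reaction as the named example (SAP 5.1). An AE dated before the imputed dose drops out of the treatment-phase numerator. The effectiveness outcome is Tanner regression or no progression (SAP 7.8.1), which needs a baseline stage. A pre-treatment Tanner record is an entry requirement (Protocol 10.4.1, criterion 4), so the rule can set aside the record that made the child eligible.

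The rules for partial dates do not help. SAP 7.1.5 keeps an AE with a missing day in the first-dose month on treatment. An AE with a complete date, which is better documented, is the one that can be lost.

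**Working it through.** The plan gives no figure to reproduce here, so the check enumerates the possible true dose days.

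**Inputs.** The imputed day is 15 (SAP 7.1.4). Baseline must be strictly before the first dose and, for CPP variables, no more than 93 days before it (SAP 7.1.1). The first analysis window opens on Day 46 (SAP Table 1). About 100 subjects are planned (SAP 6.0). The true day D is assumed uniform over 1–30 and unrelated to the timing of other records.

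**Two worked cases.**

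- True dose on the 5th, injection site reaction on the 8th. True study day: 8 − 5 + 1 = 4. Against the imputed 15th: 8 − 15 = −7. The event is in neither phase.
- True dose on the 25th, Tanner stage on the 20th. True study day: 20 − 25 = −5. Against the imputed 15th: 20 − 15 + 1 = 6. The value is not baseline, and it also precedes the first window.

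**AE k days after the true dose.** It is dated pre-treatment if D + k < 15, which holds for 14 − k of the 30 days:

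- k = 0: 14/30 = 47%
- k = 3: 11/30 = 37%
- k = 7: 7/30 = 23%
- k = 14 or more: 0

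**Assessment t days before the true dose.** It loses baseline status if D − t ≥ 15. A value dated on the imputed dose day counts as lost, because it is not prior to the dose. This holds for 16 − t of the 30 days:

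- t = 3: 13/30 = 43%
- t = 7: 9/30 = 30%
- t = 16 or more: 0

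**Month length.** For k = 3 the AE figure is 39%, 37% and 35% in months of 28, 30 and 31 days. For t = 3 the assessment figure is 39%, 43% and 45%.

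**Reverse errors.** The same inequalities apply. An AE 3 days before the true dose is counted as on treatment if D − 3 ≥ 15, 13/30 = 43%. An assessment 3 days after the true dose becomes eligible as baseline if D + 3 < 15, 11/30 = 37%.

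**93-day limit.** An assessment m days before the true dose falls outside the limit of the imputed date if 15 − (D − m) > 93, that is D < m − 78. For m = 86 this is 7/30 = 23%; for m = 93 it is 14/30 = 47%.

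**Number of children.** The share lacking the dose day is not in the documents. Assume 1%, 5%, 10% or 20% of 100, and that each such child has a fully dated AE 3 days after the dose and an assessment 3 days before it. Multiplying 1, 5, 10 or 20 children by 11/30 gives 0.4, 1.8, 3.7 or 7.3 with the AE moved to pre-treatment. Multiplying by 13/30 gives 0.4, 2.2, 4.3 or 8.7 with that assessment lost as baseline. Few children will have both records, so these lean high.

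**The case against.** The strongest reply is that this may never happen. The first-dose date is a specified data item (Protocol 10.2.2.19), logic checks look for inconsistent, missing or unclear dates and lead to site queries (Protocol 10.6.1), and records are verified against source (Protocol 10.8.1). Imputed dates and all AEs are listed, and SAP 7.1.4 allows special cases to be handled on clinical judgement. A chart that dates an injection site reaction exactly will often reveal the injection date as well. All this stands as a reason to expect few cases. It does not supply a rule: none of these provisions requires the imputed date to be checked against complete dates, and this conflict can be foreseen.

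A second reply is that the midpoint errs both ways. That also stands. A reader might infer that the rule biases the AE rate downwards. The documents do not support this, because pre-dose AEs can enter the treatment phase as well. The two losses shown above also cannot arise in the same child: the AE loss needs a true day before the 15th, the baseline loss a true day after it.

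A third reply is that the true side of the dose may itself be unknown. For Tanner and hormone values it is documented, since pre-treatment records are collected as such and required for entry (Protocol 10.2.3.1 and 10.4.1). For AEs a reader might infer the same, but AEs appear in both the pre-treatment and the on-treatment lists (Protocol 10.2.3.1 and 10.2.3.2), and the documents describe no before-or-after field for them. A bound from an AE can therefore be used only where the chart shows which side it is on.

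**Conclusion.** The point holds as a minor gap in specification. As written, SAP 7.1.4 can reverse the order of a fully dated record and the first dose, and neither the partial-date rules in 7.1.5 and 7.1.7 nor the special-cases sentence prevents it. For ordering errors, the record must lie within about two weeks of the true dose; the 93-day limit is a separate route.

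The percentages are conditional on a missing dose day and rest on a uniform true day. The number of affected children is unknown and may be zero, so no effect on the overall rates can be stated. It would also go too far to say that a displaced assessment makes the Tanner outcome missing: that happens only when no other value lies within 93 days before the imputed date. Otherwise another value takes its place. Nor are these children with complete records; the dose day is missing by definition.

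**What to change.** Amend SAP 7.1.4 so that the 15th is a default, used only within bounds set by complete dates whose side of the first dose is documented:

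- The imputed first dose is later than the last assessment documented as pre-treatment. Alternatively, an assessment documented as pre-treatment and dated on the imputed dose day is kept as baseline. Wording such as on or after would not be enough by itself, because it could put that assessment on Day 1, which SAP 7.1.1 does not accept as baseline.
- The imputed first dose is on or before the first AE or assessment documented as on treatment.
- If the 15th lies outside the bounds, take the nearest date that preserves the known order.

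In the second worked case this gives the 21st, or the 20th with the same-day value kept as baseline. In the first, if the reaction is documented as following the injection, it gives the 8th.

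If any child is affected, repeat the primary analyses with the earliest and the latest admissible dates. This also shows any effect of the 93-day limit, which the ordering bounds alone do not remove. No separate cap on an imputed last dose is needed for phase assignment, because SAP 7.1 already ends the treatment phase at the first dose of another GnRH agonist when that is earlier.

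The cost is a short addition to the SAP, a little extra programming and one sensitivity analysis that runs only if a case exists. Records whose side of the dose is documented then keep their order; for the others the uncertainty remains, and the sensitivity analysis shows its size.

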#### 7.1.5 Conventions for Missing Adverse Event Dates

Partial dates will be presented as recorded in the listings. Missing and partial AE start dates will be imputed only to determine the relationship between the start date of the event and the first dose date of ENANTONE. The following methods will be used to impute missing or partial dates of AE start dates and end date:

- AE start date month/year available and day missing:
  - If the month and year are the same as those in the first dose date, then first dose date is to be used to impute the AE start date.
  - If the month and/or year are different from those in the first dose date, then first day of the month will be used for the start date.
- AE start date year available and month/day missing:
  - If the year is the same as the year of the first dose, then first dose date is to be used to impute the AE start date.
  - If the year is not the same as the year of the first dose date, set the start date as January 1.
- AE start date completely missing:
  - The first dose date is to be used to impute the AE start date.

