## **7.11 Safety Analysis**

Safety data will be summarized using the safety analysis set, and individual data will be presented in data listings. Safety outcomes will be analyzed by ENANTONE treatment (high, low dose and overall), and unless specified otherwise will not be stratified by sex. Separate summaries will be performed for the ENANTONE treatment phase and the different segments of the follow-up phase described in section 7.8.

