### **7.11.1 Adverse Events**

The primary safety outcome is the incidence per 100 person years of AEs and SAEs. All AEs and SAEs will be coded using the MedDRA coding dictionary. AEs and SAEs will be summarized together and separately at both MedDRA levels system organ class (SOC) and

preferred term by tabulating the numbers of events, the number of patient person years at risk and incidence per 100 person years (based on the numbers of events). Furthermore, overall total number of events, person years at risk, and incidence per 100 person years (ie, any AE/SOC at any time) will be provided.

The following AE subsets will be similarly tabulated. And system organ class and preferred terms will be sorted in decreasing frequency based on the number of subjects with adverse events in total, male, and female group:

- a) AEs related to ENANTONE treatment
- b) Most frequent AEs, all AEs with incidence of 3% or greater
- c) AEs/SAEs resulting in treatment discontinuation
- d) AEs by sex

All AEs will be presented in data listings.

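### The SAP's imputation of missing AE start dates refers only to the first ENANTONE dose, so assignment of such events to treatment or follow-up is unspecified and, if the imputed dates are used for it, can shift events only from follow-up into treatment

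*SAP*

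**What the plan says.** SAP 7.1.5 limits the imputation to one purpose: dates are "imputed only to determine the relationship between the start date of the event and the first dose date of ENANTONE". Its rules have three tiers.

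- **Day missing:** the first dose date if the event falls in the first-dose month; otherwise "then first day of the month will be used for the start date".
- **Month and day missing:** the first dose date if the event falls in the first-dose year. Otherwise: "If the year is not the same as the year of the first dose date, set the start date as January 1".
- **Completely missing:** "The first dose date is to be used to impute the AE start date".

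The section announces rules for AE end dates as well but gives none.

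SAP 7.1 ends the treatment phase later, with data "up to and including either 45 days, inclusive, after the last dose or date of first dose of a non-ENTANTONE GnRH agonist therapy", whichever comes first. Everything after that is follow-up. SAP 7.11.1 states: "The primary safety outcome is the incidence per 100 person years of AEs and SAEs". SAP 7.11 adds: "Separate summaries will be performed for the ENANTONE treatment phase and the different segments of the follow-up phase". Protocol 10.3 and 10.9 state that missing data will not be imputed.

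**The concern.** A rate per phase needs every event to be placed in a phase. The imputation answers a different question, namely whether the event began before or after the first dose. Nothing in 7.1.5 refers to the last dose or to the end of the treatment phase, although SAP 7.1.4 treats the last-dose date as about as important as the first for indexing subject data.

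This leaves two possibilities. If the stated purpose is taken literally, the SAP does not say how an AE with a missing or ambiguous date enters the phase tables, and a primary outcome then rests on an undocumented programming choice. If the imputed dates are used, because they are the only AE dates the SAP supplies, events can move from follow-up into treatment. An AE that arose on another GnRH analog after ENANTONE could then be counted against ENANTONE. The study is meant to support long-term use (Protocol 13.0) and now has about 100 subjects (SAP 6.0), so a few misplaced events could be visible in the follow-up rate.

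**Working it through.** The plan gives no expected AE rate, no share of incomplete dates and no follow-up length. There is therefore no figure to reproduce, and the check applies the 7.1.5 rules literally.

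**Direction.** For an event that truly began on or after the first dose, each tier gives either the first dose date or the earliest date consistent with the recorded month or year. The imputed date is never later than the true one. A treatment event therefore cannot move into follow-up, while a follow-up event can move into treatment.

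**Which follow-up events move.**

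- Completely undated: all of them, to Day 1.
- Year only: those in the calendar year that contains the boundary. In a later calendar year, 1 January is already after the boundary, so the event stays in follow-up.
- Day missing: those in the boundary month only.

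**Share that moves.** Let F be follow-up in years (at least 1), with follow-up events spread evenly over it and the boundary equally likely on any day of the year. On average half a year of follow-up lies in the boundary year and half a month (1/24 year) in the boundary month. Hence:

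- year only: 0.5/F
- day missing: (1/24)/F
- completely undated: 1

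A simulation of 100,000 events per scenario agreed. It used treatment of 9 or 24 months, a boundary at last dose + 45 days, and first doses spread over four calendar years. No treatment event moved to follow-up or to before the first dose.

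| F (assumed) | Year only moved | Day missing moved |
|---|---|---|
| 1 | 50% | 4% |
| 2 | 25% | 2% |
| 3 | 17% | 1.4% |
| 5 | 10% | 0.8% |
| 10 | 5% | 0.4% |

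**Effect on the follow-up rate.** Person-years do not change, so the proportional fall is

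(share day-missing × fraction moved) + (share year-only × fraction moved) + share undated.

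For shares of 10%, 5% and 2% with F = 1: 0.10 × 0.040 + 0.05 × 0.501 + 0.02 = 0.049, or 4.9%. The shares are assumptions:

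| Day missing / year only / undated | Fall, F = 10 | Fall, F = 1 |
|---|---|---|
| 5 / 2 / 1% | 1.1% | 2.2% |
| 10 / 5 / 2% | 2.3% | 4.9% |
| 20 / 10 / 5% | 5.6% | 10.8% |
| 30 / 20 / 10% | 11.1% | 21% |

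The start of another GnRH analog as the boundary, and the division of follow-up into segments, were not simulated.

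**End date.** Protocol 10.2.3.1 includes AEs among the data collected before ENANTONE starts. Take such an AE with no start date and a recorded end before the first dose. SAP 7.1.5 gives it the first dose date as its start, which is after its end, and so classes it as beginning on treatment. The before/after question is then answered wrongly although the record answers it.

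**The case against.** The strongest reply is that 7.1.5 restricts the imputed dates to the relationship with the first dose, so on its wording it moves nothing across the later boundary. That stands, and it makes the shift conditional. It does not remove the gap, because no other AE rule fills it. SAP 7.1.7 offers a similar pull-back for 3-month safety intervals, but it is permissive, covers other dates, has no tier for completely missing dates and does not mention the last dose.

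There are also safeguards. Protocol 10.6.1 provides for checks and queries on missing or inconsistent dates. Partial dates are listed as recorded, and all AEs are listed. Moving events between phases does not lower the rate over both phases combined, and the study is descriptive. These points reduce the consequence, but they do not say which phase table an ambiguous event enters.

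Three stronger readings are tempting, and the documents do not support them.

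- A reader might infer that every incomplete date goes to the first dose or 1 January. The day-missing tier uses the first of the recorded month, and year-only events after the boundary year stay in follow-up.
- A reader might take one example as the size of the bias. With a last dose on 30 June, the boundary is 14 August (day 226), and (365 − 226)/365 = 38% of that year is follow-up. This is a share of one calendar year under a chosen date, not a fall in the rate.
- A reader might think that using the AE end date would return events to follow-up. It caps the onset, so it can only leave the start unchanged or make it earlier. Its value is in settling pre-dose and treatment-phase events.

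**Conclusion.** The point holds as a gap with a conditional, one-way bias. SAP 7.1.5 does not provide for the treatment/follow-up boundary on which the primary safety tables depend. If its imputed dates assign phase, the follow-up rate can only be lowered and the treatment rate only raised by the transfer. The size cannot be determined from the documents. The range of about 1% to 21% rests on assumed shares of incomplete dates, follow-up of 1 to 10 years and events spread evenly over follow-up. A statement that the follow-up rate will be too low goes further than the documents allow.

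The end-date defect does not depend on that condition: the rule can fail its own stated purpose for an AE that ended before treatment. Overall this is a minor point, but one that is cheap to settle before analysis.

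**What to change.** Amend SAP 7.1.5 as follows.

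1. Do not impute a start date later than a known AE end date, and supply the end-date rule that the section announces.
2. Assign each AE to ENANTONE treatment, other-GnRHa interval or follow-up by comparing the known date parts, the AE end date and, where available, the visit at which the AE was first recorded with the boundary in SAP 7.1. The qualifier on visits is needed: visit dates are a variable in Protocol 10.2.2.18 but are listed for the pre-treatment period (10.2.3.1) and not for treatment and follow-up (10.2.3.2).
3. Where more than one phase remains possible, keep the event in treatment as the primary rule, report the number of such events, and give one sensitivity table that counts them in the later phase.
4. Reconcile the date imputation with the statement in Protocol 10.3 and 10.9 that missing data will not be imputed, for example by recording it in SAP 7.13 as a change from the protocol.

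The cost is SAP wording, a little extra programming and one table. No new data collection is needed.

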10.2.2.8 Prior and Concomitant Medications

The dose and route of administration, start/stop date (including information on whether or not the start date was before the first dose of ENANTONE), and indication name of any medications used by the patient will be recorded.

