10.2.3.1 Variables Collected Prior to ENANTONE Treatment Initiation

- Informed consent
- Patient demographics
- Disease history
- BMD (z-scores)
- Bone age and growth rate
- Height, predicted adult height, and weight
- Medical history and comorbidities
- Prior and concomitant medications
- Evaluation of long term effect on reproduction
 - Menstruation cycles (females)
 - Pelvic measurement
 - Sexual characteristic examination

- Hormonal measurements
- β -HCG (females)
- Pregnancy
- Tanner staging
- Cranial CT/MRI
- Clinical laboratory test
- Serum markers of bone metabolism
- GnRH stimulation test
- Physical examination
- Date of visits and/or hospitalizations
- Adverse events

10.2.3.2 Variables Collected During ENANTONE Treatment Phase, Follow-up Phase and GnRHa Treatment Intervals

- Vaginal bleeding (females)
- BMD (z-scores)
- Bone age and growth rate
- Height, predicted adult height and weight
- Medical history and comorbidities
- Prior and concomitant medications
- Evaluation of long term effect on reproduction
 - Menstruation cycles (females)
 - Pelvic measurement
 - Sexual characteristic examination
 - Hormonal measurements
 - β -HCG (females)
 - Pregnancy
- Tanner staging
- Cranial CT/MRI
- Clinical laboratory test

- Serum markers of bone metabolism
- GnRH stimulation test
- Physical examination
- ECG
- Drug administration for CPP treatment (refer to Section 10.2.2.19)
- Adverse events
- Study Completion

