#### 7.1.6 Conventions for Missing Concomitant Medication / Medical History Dates

Missing or partial start dates for concomitant medications (CM) / medial history (MH) will be imputed similarly to the strategy given in section 7.1.5.

For end dates for concomitant medications, the following methods will be used to impute missing or partial dates:

- CM/MH end date month/year available and day missing:
  - The last day of month is to be used to impute the end date.
- CM/MH end date year available and month/day missing:
  - The December 31 is to be used to impute the end date.
- CM/MH end date completely missing:
  - The last visit date is to be used to impute the end date.

Note: The imputed date will not be beyond the patient's last visit date.

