## 7.6 Medication History and Concomitant Medications

Medication start and stop dates will be compared to the date of first dose of ENANTONE and will be classified as medications taken prior to, concomitant with and concomitant after ENANTONE.

Prior medications are those medications that start and stop prior to the date of first dose of study treatment. Concomitant medication with ENANTONE is any drug given in addition to the study medication, ENANTONE, and defined as those medications that are given on or after the first day of study treatment during the ENANTONE treatment phase. Medication given after ENANTONE is defined as those medications that are given on or after the last dose of ENANTONE and during the follow-up phase. Medications will be classified according to the World Health Organization Drug Dictionary (WHODRUG) and tabulated by WHO drug Anatomical Therapeutic Chemical (ATC) classification based on the safety analysis set. ATC will be sorted using alphabetical order and preferred medication names will be sorted by decreasing frequency based on the total number of all subjects.

Individual subject medication history and medication data will be listed.

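### Three of the five adverse-event start-date rules in SAP 7.1.5 impute the first dose date without checking the recorded end date, so an event that ended before ENANTONE would be counted as on-treatment

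*SAP*

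**What the plan says.** SAP 7.1.5 limits the purpose of the imputation: start dates are "imputed only to determine the relationship between the start date of the event and the first dose date of ENANTONE". It then gives five branches.

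- **Day missing, month and year known.** "If the month and year are the same as those in the first dose date, then first dose date is to be used"; otherwise the first of the recorded month is used.
- **Only the year known.** The first dose date is used if the year equals the first-dose year; otherwise 1 January of the recorded year.
- **Start wholly missing.** "The first dose date is to be used to impute the AE start date".

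The sentence introducing these branches mentions end dates as well as start dates, but no branch imputes an end date or uses one as a condition.

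Other relevant text:

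- Protocol 10.2.3.1, headed "Variables Collected Prior to ENANTONE Treatment Initiation", has adverse events as its last item.
- SAP 7.1 starts the ENANTONE treatment phase at the first dose.
- SAP 7.11.1 makes the AE and SAE rate per 100 person-years, based on event counts, the primary safety outcome.
- SAP 7.1.6 says that missing or partial start dates for medications and medical history "will be imputed similarly to the strategy given in section 7.1.5".

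**The concern.** The imputation exists to answer one question: did the event start before or after the first dose? A recorded end date before the first dose answers it with certainty, whatever is known about the start. Three branches ignore that answer and put the event on Day 1. It then falls in the treatment phase and in the numerator of the primary safety rate, although it was over before any exposure.

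The error runs in one direction. These branches can move a pre-treatment event into the treatment phase, but they cannot move an on-treatment event out of it. With the sample cut to about 100 subjects, counts for SAEs or single preferred terms may be small, and one misplaced record could then be visible in a rate.

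**Working it through.** The plan gives no figure on this point, so there is nothing to reproduce. The check has two parts: apply the branches as written, then size the effect of one misplaced event.

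**1. The branches applied as written.** Take a first dose on 20 June 2010 (illustrative) and five events, all ended before that date.

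| Recorded start | Recorded end | Imputed start | Class under the rule |
|---|---|---|---|
| June 2010 | 10 June 2010 | 20 June 2010 | on-treatment (wrong) |
| 2010 | 15 March 2010 | 20 June 2010 | on-treatment (wrong) |
| missing | 5 November 2009 | 20 June 2010 | on-treatment (wrong) |
| May 2010 | 10 June 2010 | 1 May 2010 | pre-treatment (right) |
| 2009 | 15 March 2010 | 1 January 2009 | pre-treatment (right) |

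The first three rows follow from the rule itself. If the imputed start is the first dose date D and the recorded end E is before D, the event is always classed as on-treatment, with a start after its own end. Running every pair of first-dose day and earlier end day in a 365-day year confirms this:

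- Same-year branch: 365 × 364 / 2 = 66,430 pairs, of which 66,430 are misclassified.
- Same-month branch: seven 31-day months give 7 × 465 = 3,255, four 30-day months give 4 × 435 = 1,740, and February gives 378. The total is 5,373 pairs, of which 5,373 are misclassified.
- Wholly missing start: misclassified whenever E is before D.

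**2. Whether another rule catches these records.**

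- SAP 7.1.4 leaves special cases to the programmers, but it deals with ENANTONE administration dates.
- The cap in SAP 7.1.6 keeps imputed medication and medical-history dates from passing the last visit. It does not cover AE start dates.
- Protocol 10.6.1 plans computer checks for inconsistent or missing dates. These act on entries as recorded. A start of June 2010 with an end of 10 June 2010 is consistent as recorded, and the conflict appears only after imputation.

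None of these supplies the end-date condition.

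**3. Size per misplaced event.** Inputs: about 100 subjects (SAP 6.0), a minimum of 9 continuous months of treatment (SAP 4.4), and an assumed mean duration, because the documents give none.

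Person-years = 100 × months / 12. Addition to the rate = 100 / person-years.

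| Assumed mean duration | Person-years | Added per 100 person-years |
|---|---|---|
| 9 months | 75 | 1.33 |
| 24 months | 200 | 0.50 |
| 36 months | 300 | 0.33 |

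In relative terms, one misplaced event added to k true events raises a rate by 1/k, whatever the person-years: 50% for k = 2, 20% for k = 5, 5% for k = 20. These values of k are illustrations, not expectations.

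**4. The same examples after the fix.** If an imputed start may not be later than the recorded end, the first three rows become pre-treatment and the last two do not change.

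**The case against.** **The default is a reasonable one.** Imputing to the first dose is a usual cautious choice when the end date is missing or falls on or after the first dose, and it counts against the drug rather than for it. That stands. The gap is only that the default also applies when the recorded end rules it out.

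**Few records, perhaps none, may be affected.** The error needs a pre-dose event recorded as an AE, a start that is wholly missing or matches the first-dose month or year, and an end date precise enough to fall before the first dose. Protocol 10.2.2 says variables may be collected as the chart allows, Protocol 12.1 ties an AE to a subject who has been given a medicinal product, and Protocol 10.2.2.7 records medical history separately. A reader might infer that pre-dose AEs are certain to be in the data. The documents support only that they may be.

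**The rule is not wrong throughout.** A reader might infer that every partial start goes to the first dose date. Two of the five branches do not do this, and they classified the examples correctly.

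**A start after its own end does no harm by itself.** Listings show partial dates as recorded, and no analysis of AE duration is planned. This is accepted; what matters is the before/after classification.

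**Medications.** A reader might infer that the rule overwrites the CRF item "including information on whether or not the start date was before the first dose of ENANTONE" and so misclassifies prior drugs. The text does not go that far. SAP 7.1.6 asks for a similar strategy, not an identical one, and SAP 7.6 compares stop dates as well as start dates: "Prior medications are those medications that start and stop prior to the date of first dose of study treatment". A drug with a recorded pre-dose stop and a start imputed to Day 1 would not fit that definition, but it would not clearly fit the definition of concomitant use either. This is an ambiguity in a descriptive table.

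**Conclusion.** The point holds for three of the five branches in SAP 7.1.5. As written, they class an AE with a recorded pre-dose end as on-treatment and count it in the primary AE/SAE rate, and nothing else in the documents prevents this. It is a stated rule that gives a wrong answer, not merely a missing detail.

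The direction is known: the rate can only rise. The total effect is not known, because the documents do not say how many records qualify, and the number may be zero or small. Per event the addition is about 0.33 to 1.33 per 100 person-years. That range assumes 100 subjects and mean treatment of 36 down to 9 months, and applies to the overall column. A dose-group column, with fewer person-years, would show a larger addition per event. The documents do not support a claim that the reported safety rate will be materially inflated.

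The medication issue is secondary and does not reach the primary safety rate.

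**What to change.** Add to SAP 7.1.5:

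> If the recorded AE end date (complete, or partial but sufficient to show it) is before the first ENANTONE dose, the event is classed as pre-treatment. An imputed start date may not be later than the recorded end date.

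As a secondary clarification, apply the same end-date limit to start dates in SAP 7.1.6, and state that the CRF answer on whether a medication began before the first dose is used when its start date is imputed. This affects descriptive medication and medical-history tables only.

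The cost is a few sentences in the SAP and one condition in the derivation program. No new data are needed. Events with a missing end date, or an end on or after the first dose, keep their present classification, so the treatment-phase AE count can only fall or stay the same.
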